**Table 3 Study Objectives and Endpoints**

Objectives	Endpoints
Primary	

Assess the safety and tolerability profile, including immunogenicity, of JK07, administered IV according to protocol-defined dosing regimen.

	

Incidence and severity of TEAEs and their relationship to the IP.

12-lead ECG parameters (heart rate, PR, QRS, QT, QTcF) change from baseline derived as mean from triplicate ECG recordings as well as QT and QTcF outlier analyses.

Change from baseline in the incidence of rhythm abnormalities (retrieved from telemetry readings for 48 hours postdose).

Laboratory parameters – change from baseline each assessment time point per Table 1 SoA postdose: hematology, chemistry, coagulation, and lipid panels.

Immunogenicity

Incidence of early and delayed-type hypersensitivity responses.

Presence of serum anti-JK07 antibodies (confirmed positive antibody response, titer, neutralizing antibodies).

Vital signs – change from baseline in vital signs and the relationship to JK07 compared with placebo, including:

Blood pressure (BP)

Temperature

Heart rate (HR)

Respiratory rate (RR)

Secondary	

To determine the PK characteristics of JK07 administered IV according to protocol-defined dosing regimen.

	

PK parameters of intact JK07 including, but not limited to, maximum concentration (<math>C_{max}</math>), time to <math>C_{max}</math> (<math>t_{max}</math>), area under the concentration-time curve to the last quantifiable concentration and extrapolated to infinity [<math>AUC_{(0-\text{last})}</math> and <math>AUC_{(0-\infty)}</math>], half-life (<math>t_{1/2}</math>), elimination rate constant (<math>\lambda_z</math>), systemic clearance (CL), and volume of distribution (<math>V_z</math>). Surrogate measurement of intact JK07 to be carried out through detection of both the JK07 antibody domain and the JK07 NRG-1 peptide fragment in the evaluation of PK parameters.

Exploratory	

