### 8.2 Safety Assessments

Planned time points for all safety assessments are provided in Table 1, and Table 2, and Appendix 3, Table 13 and Table 14.

Subjects will be observed for injection site reactions until Day 4 following IP administration, for DLAEs until Day 15 following IP administration, and for AEs and SAEs from the time of informed consent until 30 days after the IP administration. Following Day 30, only SAEs deemed at least possibly related to the study drug or study procedures will be collected until the End of Study visit (Day 180).

The safety of JK07 in patients with heart failure with reduced ejection fraction will be evaluated based on criteria described by the CTCAE Version 5.0.

The investigator will monitor the occurrence of all AEs during the first 30 days after administration of the study drug. All AEs must be recorded in the source documents and on the appropriate page(s) of the case report form. All SAEs including any deaths, which occur up to and including 30 days after administration of the study drug, must be reported to the Medical Monitor within one working day, whether or not considered causally related to the study drug. Following the first 30 days, only SAEs deemed at least possibly related to the study drug or study procedures should be collected and reported as such. All AEs and SAEs will be followed until resolution, stabilization, until the event is otherwise explained, until the end of their participation in the study, or until the subject is lost to follow-up.

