## 8.2.2 Injection Site Assessment

The site of infusion of the study drug will be assessed for local reactions at the times shown in the SoA (Table 1). Any findings (or lack thereof) will be documented in the subject's eCRF. During Day 1 (1 early assessment and 1 late assessment/end of the day), the Investigator may choose to evaluate the infusion site as deemed appropriate.

Infusion site evaluations will be made by clinical staff as described below; if an injection site reaction greater than that typically expected for the insertion of an IV line is observed, a physician will characterize and document the reaction as an AE. The infusion site will continue to be reviewed at the time points indicated in the SoA (Table 1), or until the AE is resolved.

Infusion sites will be monitored for pain, tenderness, erythema and swelling. Each infusion site reaction will be categorized using the intensity grading scheme presented in [Table 6](#); the intensity of each resulting AE will be categorized as described in (e.g., at least moderate intensity injection site reaction may be recorded as a mild AE if considered appropriate according to the Investigator's judgement).

**Table 6** Injection Site Reaction Grading Scheme

Reaction	Intensity Grading				
	Absent (0)	Mild a (1)	Moderate a (2)	Severe a (3)	Potentially Life-threatening (4)
Pain	Absent	Does not interfere with activity	Repeated use of non-narcotic pain reliever or prevents daily activity	Any use of narcotic pain reliever or prevents daily activity	Hospital visit (A and E) or hospitalization
Tenderness	Absent	Mild discomfort to touch	Discomfort with movement	Significant discomfort at rest	A and E visit or hospitalization
Erythema/redness	Absent	2.5 to 5.0 cm	5.1 to 10.0 cm	>10.0 cm	Necrosis or exfoliative dermatitis
Induration/swelling	Absent	2.5 to 5.0 cm and does not interfere with activity	5.1 to 10.0 cm or interferes with activity	>10.0 cm or prevents daily activity	Necrosis
Other b	Absent		Present		

Abbreviation: A and E; adverse event.

a Measurements refer to the reaction at the greatest single diameter.

b Any other reactions such as bruising, itching, or ulceration will be recorded as absent or graded as to severity.

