## 9.0 STATISTICAL CONSIDERATIONS

### 9.1 Statistical Hypotheses

Formal statistical hypothesis testing is not planned for this study. All analyses will be considered exploratory and descriptive.

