#### **9.4.3 Safety Analyses**

All safety analyses will be performed on the Safety Population.

All safety data will be listed according to treatment group, subject number, and visit.

The AEs are defined in [Section 8.3.1](#). The DLAE are defined in [Section 4.6](#).

AEs will be coded using the Medical Dictionary for Regulatory Activities (MedDRA) Version 22. The number of AEs and incidence rates will be tabulated by preferred term and system organ class.

The AEs will be coded by maximum severity, relationship to study treatment, as SAEs or DLTs as needed, and will be categorized and tabulated for each treatment group (cohort).

DLAEs will be presented in the same manner as the AEs.

Incidence of injection site reactions will be summarized by treatment group, and if appropriate by assessment time.

All laboratory test results, vital signs measurements, ECG results, weight, and body mass index will be summarized for each treatment group using descriptive statistics at each visit for raw numbers and change from baseline. The incidence of treatment-emergent abnormal laboratory, vital sign, and ECG values will also be summarized using descriptive statistics.

For 12-lead ECG parameters (HR, PR, QRS, QT, QTcF), the 90 % confidence interval will also be presented for each parameter mean and change from baseline values. Outliers for QT and QTcF defined under outcome measures will be summarized using counts and percentages by treatment and sampling time, if appropriate and using subject-level maximum over time by treatment. The following categories will be presented by treatment and overall, for JK07:

- outlier QT and QTcF intervals (450-480 ms, 480-500 ms and >500 ms)
- change from baseline in QT and QTcF intervals (30-60 ms and >60 ms)

Additional corrections to QT may also be similarly analyzed. If relevant, analysis excluding ECGs capturing paced beats will be performed.

Abnormal findings on 12-lead ECG will be summarized by treatment using descriptive statistics.

All recorded ECGs will be interpreted on site and subsequently collected, digitized, and sent for central laboratory standardized measurements. The incidence (number of subjects and percent) of a confirmed positive ADA response will be summarized by treatment. The incidence of neutralizing anti-drug antibody response will also be summarized, if appropriate.

All data will be provided in data listings sorted by treatment group, subject number, and visit.

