## **B. Adverse Events**

An adverse event (AE) is defined as any untoward medical occurrence in a clinical study subject administered a pharmaceutical product, which does not necessarily have a causal relationship with the study IP. A treatment-emergent adverse event (TEAE) is defined as an AE that started or worsened in severity on or after the date of the IP administration (Day 1). All AEs will be coded using the Medical Dictionary for Regulatory Activities (MedDRA) Version 22.1 and will be summarized by System Organ Class (SOC) and Preferred Term (PT).

All adverse events will be graded using the Common Terminology Criteria for Analysis Events (CTCAE) Version 5.0, ranging from 1 to 5: Grade 1 (Mild), Grade 2 (Moderate), Grade 3 (Severe), Grade 4 (Life threatening or disabling), or Grade 5 (Death). If the grade is missing for a TEAE, the event will be counted as grade 3 in the summary tables.

Subjects will be observed for possible allergic reactions following the treatment and will be monitored for DLAEs throughout the study. All AEs, including SAEs, will be collected from the time of enrollment until 30 days after the treatment. Following the first 30 days, only SAEs that are at least possibly related to the treatment or study procedures will be collected.

An overall summary for subjects with AEs will be summarized by cohort (each dose level of JK07 and the placebo group pooled across all the treatment groups) including the following subsets. The number of events and subjects will be included.

- **AEs**
- **TEAEs**
- TEAEs related to study drug. This subset includes TEAEs with a drug relationship of “possibly related” and “definitely related”, or a missing drug relationship.
- Serious TEAEs
- Serious TEAEs related to study drug. This subset includes Serious TEAEs with a drug relationship of “possibly related” and “definitely related”, or a missing drug relationship.
- TEAEs leading to study drug permanent discontinuation
- TEAEs leading to study drug infusion interruption. This subset includes TEAEs with an answer “Yes” to the question “Was infusion interrupted?” on the Infusion Drug Administration form.
- Treatment-emergent infusion site reactions. This subset includes TEAEs with an answer “Yes” to the question “Was this an infusion site reaction?” on the AE form
- TEAES by maximum grade. Only present the number of subjects for this subset.

- **DLAEs**

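### The SAP tabulates infusion-site reactions only when they were reported as AEs, an undeclared narrowing of the incidence summary planned in Protocol 9.4.3

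*SAP*

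**What the plan says.** The protocol uses injection site and infusion site interchangeably. Section 8.2 sets the observation period: "Subjects will be observed for injection site reactions until Day 4 following IP administration". The Schedule of Assessments (Table 1) marks a check on Days 1, 2, 3 and 4.

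Section 8.2.2 describes the data. "Any findings (or lack thereof) will be documented in the subject's eCRF", so absence of a reaction is recorded as well as presence. "Each infusion site reaction will be categorized using the intensity grading scheme presented in" Table 6, which runs from 0 (absent) to 4 (potentially life-threatening). A physician documents an AE only "if an injection site reaction greater than that typically expected for the insertion of an IV line is observed". The same section allows a reaction of at least moderate site intensity to be entered as a mild AE.

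The planned analysis is in Protocol 9.4.3, in a sentence separate from those on AEs and DLAEs: "Incidence of injection site reactions will be summarized by treatment group, and if appropriate by assessment time".

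SAP VII.B handles the topic only through AE records. Its overall AE summary has this row: "Treatment-emergent infusion site reactions. This subset includes TEAEs with an answer" of yes to the AE form's infusion-site question. DLAEs have a matching row. The tables by System Organ Class and Preferred Term add TEAEs and SAEs with an infusion-site reaction. AE severity is CTCAE version 5.0; the SAP does not mention Table 6. SAP I.B gives the SAP precedence over the protocol, and its Changes from Protocol section covers only abnormal vital signs.

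**The concern.** The protocol sets up a dedicated local-tolerability assessment with its own schedule and grading scale, then plans an incidence summary. Only the scheduled checks have an assessment time; AEs have onset dates. The natural reading of 9.4.3 is therefore a summary of the 8.2.2 checks.

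The SAP's named tables use a narrower set of reactions. Entry to that set depends on a judgement at the site, which may vary among the roughly 8 expected centers. A reaction thought ordinary for an IV line is left out of the tables, and one that is included may carry an AE severity below its Table 6 grade.

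The filter is not needed to separate drug from procedure. Placebo is given by the same IV route over the same 60 minutes (Protocol Table 5), so the pooled placebo group shows the IV-line background directly. At stake is a clear description of local tolerability in a first-in-human IV study whose primary objective is safety and tolerability.

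**Working it through.** **Comparing the two documents**

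| Item | Protocol | SAP |
|---|---|---|
| Source of the count | 8.2.2: scheduled site checks, presence or absence recorded | VII.B: AE records only |
| Threshold to be counted | 9.4.3: none stated | Must have been reported as an AE, so greater than usual for an IV line (Protocol 8.2.2) |
| By treatment | Yes (9.4.3) | Yes, for the AE subset |
| By assessment time | If appropriate (9.4.3) | None specified |
| Severity scale | Table 6 at the site check; AE graded separately | CTCAE only |
| Declared as a change | – | No |

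Two general SAP provisions might fill the gap. SAP V.M provides for listing eCRF data, so reactions not reported as AEs may appear in a listing. SAP VII says categorical safety data will be summarized by count and percentage, but it names no infusion-site table and the same paragraph ties safety evaluation to CTCAE. Neither clearly restores the 9.4.3 summary.

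**Illustrating the size**

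The plan has no figure to reproduce. It states "Formal statistical hypothesis testing is not planned for this study", and it gives neither a reaction rate nor the share of reactions that become AEs. The inputs are therefore assumptions, apart from the group sizes:

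- p, the share of subjects with any reaction: 30% (range 20-40%), assumed.
- f, the share of those whose reaction crosses the AE threshold: 25-50%, assumed.
- n = 7 active subjects, the 1 sentinel plus 6 randomized of a fully expanded cohort (Protocol 9.6). An unexpanded cohort has 1 + 3 = 4.

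Rate seen in the SAP tables = p × f:

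- 0.30 × 0.25 = 0.075
- 0.30 × 0.50 = 0.15
- over the full range, 0.20 × 0.25 = 0.05 to 0.40 × 0.50 = 0.20

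Chance of at least one reaction among n independent subjects = 1 − (1 − rate)^n. For n = 7:

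- all reactions: 1 − 0.70^7 = 0.92
- AE subset, f = 25%: 1 − 0.925^7 = 0.42
- AE subset, f = 50%: 1 − 0.85^7 = 0.68

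For n = 4 the same rates give 1 − 0.70^4 = 0.76, against 1 − 0.925^4 = 0.27 and 1 − 0.85^4 = 0.48.

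At the ends of the assumed range, with n = 7:

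- p = 20%, f = 25%: from 1 − 0.80^7 = 0.79 to 1 − 0.95^7 = 0.30
- p = 40%, f = 50%: from 1 − 0.60^7 = 0.97 to 1 − 0.80^7 = 0.79

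**The case against.** The best defense is that 9.4.3 is a single sentence. It names no source form, does not refer to Table 6, and makes the by-time display conditional. The SAP does give an incidence by treatment group. What drops out of its tables is what the protocol itself regards as ordinary for an IV line. The table shells are in a separate document, so a suitable table may exist there. The protocol, not the SAP, allows AE severity to sit below the site grade.

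Much of this stands, and it rules out several stronger readings that a reader might infer:

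- *That a named endpoint has been redefined.* Protocol Table 3 does not list injection-site reactions. The nearest primary endpoint is "Incidence and severity of TEAEs and their relationship to the IP", which the SAP analyzes.
- *That mild reactions vanish.* The AE threshold is not a Table 6 grade. A mild but unexpected reaction is an AE and is counted. Reactions not reported as AEs may still be listed.
- *That the SAP breaks a promise to tabulate Table 6 grades.* Section 9 of the protocol makes no such promise. The grades are recorded and have no specified summary, which is a gap rather than a contradiction.
- *That dose decisions are affected.* Nothing in the documents shows this; the safety reports to the Data Review Committee are left to its charter.

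The mismatch itself remains. The 9.4.3 sentence stands apart from the AE tabulations and speaks of assessment time, and the governing document neither specifies that summary nor says it has been dropped.

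**Conclusion.** The point holds as an undeclared narrowing of a planned descriptive safety summary. Under the SAP's named tables, reactions judged no greater than expected for an IV line go uncounted, severity may be understated relative to Table 6, and there is no by-time display.

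The undercount cannot be derived from the documents. The fall from 92% to 42-68% for 7 active subjects rests on assumed rates (30% with any reaction, 25-50% of those becoming AEs) and on independence between subjects. Taking 42% alone would quote only the harsher end of that range.

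Two points remain uncertain: the table shells are not among the documents, and that the assessment data exist is inferred from the protocol's recording requirement. This should be corrected because the remedy is cheap, but no endpoint or hypothesis test depends on it.

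**What to change.** Add one table to SAP VII, built from the scheduled infusion-site assessments. It should give the number and percentage of subjects with any reaction, and by maximum Table 6 grade, for each treatment including pooled placebo and for each assessment day. Keep the existing AE-form subset and label it *reactions reported as AEs*.

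If the assessment data were not captured in usable form, say so in Changes from Protocol and justify the AE-only approach there, as the SAP already does for abnormal vital signs.

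The cost is one extra table from data the protocol already requires. One footnote is needed: in Table 6, preventing daily activity appears under both moderate and severe pain, so the maximum grade for pain is ambiguous unless the SAP states how such records are classified.

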### **C. Clinical Laboratory Results**

Laboratory test results include hematology; chemistry (including serum glucose on the Fingerstick Glucose Multi - Local form in the CRF); coagulation, urinalysis, analyzed by the local labs and collected in the EDC system. The severity of laboratory abnormalities will be graded using the CTCAE whenever possible.

Summaries of actual values and changes from baseline will be summarized descriptively by treatment group and overall for each scheduled visit and each timepoint where applicable.

For all laboratory tests, shift tables summarizing the Principal Investigator’s assessment of abnormality – i.e. Normal, Abnormal Clinically Significant (CS), Abnormal Non-Clinically Significant (NCS) – will be displayed. The counts and percentages of subjects who were normal at baseline and became abnormal subsequently, or the opposite, will be presented.

All laboratory test results will be presented in by-subject listings, with collection date, result and unit, normality and clinical significance, change from baseline, and the CTCAE grading wherever possible, at each visit and timepoint (where applicable). Abnormal results will be presented in a separate listing.

### **D. Vital Signs**

Vital sign parameters, including the weight, body temperature, heart rate, respiratory rate, and systolic and diastolic blood pressure, will be summarized using descriptive statistics by cohort at each visit, by treatment group (and placebo) and overall. Absolute values and changes from baseline will be presented.

Vital signs will also be presented in a by-subject listing, detailed in result, unit, CFBL.

#### **E. Medical History**

Medical History will be coded using MedDRA version 22.1, and will be summarized by System Organ Class (SOC) and Preferred Term (PT) for the Safety Evaluation Population by treatment group and overall.

Medical History will also be presented in a by-subject listing, detailed in SOC, preferred term start date, and end date (or ongoing). For each subject, the subject number will be displayed only once.

#### **F. Surgical History**

A listing will be generated for subjects with surgical history, detailed in location, description, start date and end date.

#### **G. Electrocardiograms (Digital 12-Lead Triplicate ECGs)**

Each subject will receive triplicate, twelve-lead ECG evaluations including HR, PR, QRS, QT (uncorrected), QTcF (corrected), and an overall evaluation of normality and clinical significance during screening and starting on Day 1 following admission to the hospital. ECG data will be collected, reviewed and analyzed by a Central Reader and the Principal Investigator. Findings identified by the Central Reader will be listed only for the concerned subjects.

The triplicate measurements of each subject at each timepoint will be averaged before summary. The observed values and mean CFBL of these ECG measurements will be summarized by cohort at each timepoint using descriptive statistics including 90% confidence interval of the mean. The overall ECG evaluation results, alone with shift from baseline (from abnormal to normal, or from normal to abnormal) will be summarized in a separate table by each treatment cohort and aggregated placebo at each visit. Results collected by the Central Reader and the Principal Investigator will be displayed separately.

Categories of QT and QTcF intervals (431-450 ms and >450 ms for males, and 451-470 and >470 ms for females) and CFBL in QT and QTcF intervals (30-60 ms, and >60 ms) will be summarized using counts and percentages by cohort and sampling time. Additional corrections to QT may be analyzed in a similar way. Results collected by the Central Reader and the Principal Investigator will be displayed separately.

A significant proportion of HFrEF patients with pre-existing implanted functional atrio-ventricular (A-V sequential) pacemakers and cardiac resynchronization devices (CRT), may be unevaluable with respect to QT/QTc analysis due to the inherently prolonged and fixed QRS configuration. The presence of these devices, which include defibrillators, is not considered an increased safety risk.

The electrocardiogram analysis will be conducted by cohort in the following two groups and presented separately:

- All subjects
- Subjects not having pacemakers identified by the contents of ECG overall evaluation. If none of the ECG evaluations have the word “pace” or “paced” or “pacemaker” or “electronic” or “electronically” or “resynchronization” or “CRT” for a subject, the subject is considered not to have a pacemaker or CRT (cardiac resynchronization therapy).

A by-subject listing will be presented with observed ECG evaluations and CFBL at each visit, detailed in observation date, timepoint, value of each measurement, whether the subject had an implantable pacing device, and the overall assessment. The abnormal ECG results will be listed separately. In addition, categories of QT and QTcF records will be presented in a separate listing. An additional listing presenting Central Reader’s findings will be produced, only for subjects presenting findings.

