10. Cerebrovascular accident or hospitalizations for CV (cardiovascular) causes other than routine percutaneous procedures such as device, battery, generator changes or pacemaker lead insertion/replacement, including HF, chest pain, stroke, transient ischemic attack, or arrhythmias within 2 months prior to screening.
11. Subjects at screening have an abnormal or clinically significant 12-lead ECG abnormality, that, in the opinion of the Investigator, would affect efficacy or safety evaluation or place the subject at risk.
12. History or evidence of clinically significant arrhythmias uncontrolled by drug therapy or use of an implantable defibrillator, long QT syndrome, or evidence of QT prolongation with QTcF >450 ms for males or QTcF >470 ms for females during screening and/or prior to randomization.
13. Clinically significant renal dysfunction as measured by the estimated glomerular filtration rate of <45 mL/min/1.73m^2 as calculated by local laboratory standards (Cockcroft-Gault equation for estimation of creatinine clearance [CrCl] [Cockcroft and Gault. 1976]) at screening, or a clinically significant change in renal function between screening and baseline.
14. Clinically significant liver dysfunction as measured by: ALT >2.0 × the upper limit of normal (ULN), alkaline phosphatase > 2.0 × ULN, AST >2.0 × ULN, or GGT >2.0 × ULN or serum bilirubin ≥ 1.2 × ULN at screening, or a clinically significant change in liver function between screening and baseline.
15. Subjects with alteration of the coagulation panel (international normalized ratio [INR]) and/or prothrombin time (PT) ≥1.5 × the ULN; activated partial thromboplastin time (aPTT) ≥1.5 × ULN, or serum albumin ≤3 gm/dL. For subjects on warfarin or other anticoagulants, an INR (or PT) considered by the Principal Investigator as therapeutically appropriate will be allowed.
16. Subjects with values of total CPK and/or CK-MB >2.5x ULN per institutional standards at screening.

17. Any subject who by Investigator's judgement, has a significant hematuria or proteinuria at screening.
18. Concurrent treatment with Class Ia or III antiarrhythmic drugs (the medication must have been discontinued more than 2 months before informed consent).
19. Positive screening for human immunodeficiency virus antibodies, hepatitis B surface antigen, or hepatitis C virus antibodies.

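### The ECG shift is specified only as normal/abnormal, so a change from abnormal not clinically significant to abnormal clinically significant is not counted as a shift

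*SAP*

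**What the plan says.** SAP VII.G records for each ECG "an overall evaluation of normality and clinical significance". It then plans one table that holds the overall evaluation results and, with them, the change within subjects: "shift from baseline (from abnormal to normal, or from normal to abnormal) will be summarized in a separate table". The table is laid out by treatment cohort and pooled placebo at each visit, with Central Reader and Principal Investigator results shown separately. No movement between the two abnormal grades is named as a shift.

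For laboratory tests, SAP VII.C builds its shift tables on the investigator's assessment at three levels, "Normal, Abnormal Clinically Significant (CS), Abnormal Non-Clinically Significant (NCS"). The sentence that follows, on what will be counted, returns to two directions: "The counts and percentages of subjects who were normal at baseline and became abnormal subsequently, or the opposite, will be presented".

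Other ECG outputs are a by-subject listing that includes the overall assessment, a separate listing of abnormal ECGs, and a listing of Central Reader findings (SAP VII.G). Under Protocol 8.3.7, emergent ECG abnormalities that the investigator finds clinically significant are recorded as adverse events.

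**The concern.** A shift table exists to show change within subjects by dose group. Here the scale is coarser than the data collected. For a subject whose ECG is already abnormal at baseline, the only shift that can be recorded is an improvement; worsening in clinical significance is not counted. Even for a subject who starts normal, a shift to abnormal does not say whether the new finding is clinically significant.

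Entry rules admit subjects with abnormal ECGs. Protocol 5.2, criterion 11, excludes on judgement: "Subjects at screening have an abnormal or clinically significant 12-lead ECG abnormality, that, in the opinion of the Investigator, would affect efficacy or safety evaluation". The other ground it gives is risk to the subject. Abnormalities judged less important can enter, and these are the NCS baselines for which the two-way shift cannot register worsening. With 4 to 7 active subjects per cohort, one or two uncounted worsenings could change how a dose group is read.

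**Working it through.** The plan gives no figure to reproduce. The check is to build three-level tables and collapse them to what SAP VII.G specifies.

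**Inputs**
- Active subjects per cohort, counting the sentinel: 1 + 3 = 4 in a 5-subject cohort and 1 + 6 = 7 in a 9-subject cohort (Protocol 1.1 and 4.2).
- Pooled placebo at maximum size: 7 cohorts x 2 = 14.
- Share with an abnormal baseline ECG: not in the documents. Assumed range 30% to 90%.

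**Example 1. Seven active subjects, baseline 1 Normal, 6 NCS, 0 CS**

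| | No change | Three go NCS to CS |
|---|---|---|
| Normal to abnormal | 0 | 0 |
| Abnormal to normal | 0 | 0 |
| Visit result (Normal/NCS/CS) | 1/6/0 | 1/3/3 |
| 3x3 cell, NCS to CS | 0 | 3 |

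The shift counts do not separate the two cases. The visit results do, provided they are printed with the CS/NCS grade.

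**Example 2. Seven active subjects, baseline 1 Normal, 4 NCS, 2 CS**

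| | No change | Two go NCS to CS, two go CS to NCS |
|---|---|---|
| Normal to abnormal | 0 | 0 |
| Abnormal to normal | 0 | 0 |
| Visit result (Normal/NCS/CS) | 1/4/2 | 1/4/2 |
| 3x3 cell, NCS to CS | 0 | 2 |

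Here the shift counts and the visit results both agree across the two cases. Only the 3x3 table tells them apart.

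**Across visits.** One CS result at each of three visits can be one subject three times or three subjects once. Counts by visit cannot say which; a shift to worst post-baseline can.

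**How many subjects this touches.** Every subject abnormal at baseline is one for whom worsening is not counted. Expected number = assumed share x n:

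| Assumed share abnormal | 4 active | 7 active | 14 placebo |
|---|---|---|---|
| 30% | 1.2 | 2.1 | 4.2 |
| 50% | 2.0 | 3.5 | 7.0 |
| 70% | 2.8 | 4.9 | 9.8 |
| 90% | 3.6 | 6.3 | 12.6 |

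These are subjects whose worsening would go uncounted if it occurred, not expected numbers of worsenings.

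**Timing of the adverse event route.** Protocol 8.3.3 collects all adverse events to 30 days after dosing, and after that only serious events at least possibly related to study drug or procedures. Protocol Table 1 schedules ECGs at Days 60, 90, 135 and 180. A non-serious NCS-to-CS change first seen at one of those four visits falls outside adverse event collection.

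**The case against.** The strongest reply is that the table is more than its shift counts. It also carries the overall evaluation results at each visit, and that evaluation includes clinical significance. A reader might infer that the table cannot show worsening to clinically significant at all; the text does not support that, and Example 1 shows why. To conceal worsening at a single visit, as in Example 2, some subjects must be CS at baseline, and exclusion criterion 11 should keep them few. This stands, and it narrows the point to the within-subject shift.

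A reader might also infer that most baseline ECGs in this population are abnormal. Neither document says so. The SAP sentence that begins "A significant proportion of HFrEF patients with pre-existing implanted functional atrio-ventricular (A-V sequential) pacemakers" concerns whether such patients can be evaluated for QT/QTc; it gives no prevalence of abnormal ECGs among those enrolled. Protocol 5.1, criterion 5, limits subjects with ICDs to 15% paced beats and requires a non-paced Day 1 ECG. Protocol 8.2.5 asks for screening and baseline ECGs without pacing. The SAP also repeats the ECG analysis in subjects without pacemakers.

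Nor do the laboratory tables offer a clean contrast, since their count sentence is two-way as well. They supply the three level names, not a finished model.

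The primary ECG endpoint is change in heart rate and intervals plus QT and QTcF outliers; the overall evaluation shift is not part of that definition. Listings of 4 to 7 active subjects can be read line by line, and the table shells, kept in a separate document, may already use three levels.

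These replies lower the importance but do not close the gap. Listings give no tabulated comparison of dose with placebo, the adverse event route narrows after Day 30, and the governing SAP sentence still names only two directions.

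**Conclusion.** The point holds in a limited form. As written, the ECG shift does not count a move from NCS to CS, although the grade needed to count it is collected. This follows from the SAP wording alone and applies to any subject abnormal at baseline, whatever their share. The weakness is in the tabulated within-subject change, not in data capture, and other outputs recover part of it.

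The size cannot be fixed from the documents. Under the assumed 30% to 90% range it concerns roughly 1 to 4 of 4, or 2 to 6 of 7, active subjects in a cohort. The importance is modest: the table is descriptive, Protocol 9.1 plans no hypothesis tests, and the separate shells could not be checked.

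**What to change.** In SAP VII.G, replace the two-direction description with a 3x3 baseline-by-post-baseline shift: Normal, Abnormal NCS, Abnormal CS. Present it at each visit and from baseline to worst post-baseline, by JK07 treatment group and pooled placebo, separately for the Central Reader and the Principal Investigator. The SAP does not say whether both readers grade clinical significance; if one does not, say so and keep that reader's table at two levels. State also that the overall evaluation results by visit are shown with their CS/NCS grade.

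The cost is one or two SAP sentences and a shell edit, or only the sentences if the shells already have three levels. Where the grade is already recorded, no new data are needed.
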